Examining the effects of a posterolateral mobilization with movement compared to a posterolateral self-mobilization with movement and dynamic stretching on hip internal rotation limitations: A randomized control trial

2/16/2020

University of South Carolina Protocol

Study Title: Examining the effects of a posterolateral mobilization with movement compared to a posterolateral self-mobilization with movement and dynamic stretching on hip internal rotation limitations: A randomized control trial

Principal Investigator Name: [name]

Faculty Mentor Name (if applicable): [name]

- 1) *If there is a written grant proposal, dissertation, or thesis, or your professor has provided you with a template, you are not required to use this template. However, this template should be used as a reference so that you are aware of the issues that should be addressed.*
- 2) *Texts in italics are instructions, which should be deleted. Modify as appropriate to your study.*
- 3) *Once protocol is complete, save it as a Word document. Go back to the IRB application and upload the protocol.*

A. SPECIFIC AIMS

List the broad, long-term objectives and the goal of the specific research proposed, e.g., to test a stated hypothesis, create a novel design, solve a specific problem, challenge an existing paradigm or clinical practice, address a critical barrier to progress in the field, or develop new technology.

The goal of this study is to compare the efficacy of three clinical interventions intended to treat hip dysfunctions such as hip osteoarthritis. Physical therapists utilize mobilization with movement clinically to increase range of motion that has been limited by hip pathology. This study will compare mobilization with movement administered by a physical therapist, self-administered mobilization with movement, in which patients are instructed in the maneuver and then perform it at home, and dynamic stretching as instructed by a physical therapist. Efficacy will be judged through changes in hip internal rotation range of motion, a motion which is typically limited in patients with hip pathology.

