Surveys/Instruments, Devices, or Other Measures: Baseline bubble inclinometer to measure each participant's hip internal rotation will be used throughout the data collection. A Mulligan mobilization belt will also be used for two of the treatment groups in order to apply the mobilization at the hip required for the mobilization with movement technique.

Groups will be randomized using a random number generator with a proposed number of approximately 15-20 participants in each of the three groups. Participants will also be grouped by level of severity of the limitation in ROM, ranging from severe limitations to mild limitations. The mild limitation group will have from 25-30 degrees of IR at the hip, moderate will be 20-24 degrees, and severe will be <20 degrees. To ensure that participants are evenly spread out between the three treatment groups in regards to the severity of their limitation, they will roll a die which will determine in which of the three treatment groups they will be placed in. Only the therapist will know how the participants are grouped based on the die roll to make sure the researchers are blinded to the groups.

Data Analysis: Statistical analysis will be performed using SPSS with a Repeated Measures Analysis of Variance (ANOVA) in order to determine significance between the three groups while also using time as an outcome pre-and-post-test. Significance will be set at $p < .05$ which establishes a 95% confidence interval. A one-way ANOVA will be performed first to determine whether the groups are different at baseline, followed by a repeated measure ANOVA with a within factor and a between group factor. This will reveal the main effects of time, group, and a time by group interaction. ANOVA tests are used to determine whether there are significant measures between two or more groups and allows for comparison of multiple sample means to assess whether there is a significant difference between groups and within the same group from pre and post intervention. F values will be calculated using SPSS software to assess for any significant differences. Post-Hoc testing will be conducted if a significant F value is found in order to determine where the differences exist using three Paired t-tests, one for each group.

E. PROTECTION OF HUMAN SUBJECTS

1. TARGET POPULATION:

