Participants will be recruited through in person interview from the University of South Carolina Doctor of Physical Therapy program graduate students and Wingate Doctor of Physical Therapy program. The targeted population is college-aged individuals. Inclusion criteria will be that participants must have less than 30 degrees of hip internal rotation (HIR) in at least one hip. Previous studies have suggested that HIR of less than 30 degrees has been correlated with an increase in injuries to the lower back and lower extremities.^{21,22} Exclusion criteria will include any traumatic injury within the last six months, any known skeletal deformities limiting activity such as femoro-acetabular impingement or fractures, surgeries within the last 6 months, positive findings in the Flexion, Adduction, Internal Rotation (FADDIR) or Flexion, Abduction, External Rotation (FABER) tests for hip impingement pathology depicted in figures 3 and 4 below, and any presence of OA, rheumatoid arthritis, or neurological

University of South Carolina Protocol

conditions which could negatively impact findings. Anticipated sample size is between 45-60 participants.

2. RECRUITMENT PLANS:

Participants will be recruited through in-person interview and conversation during the Fall Seminar class for DPT students. The study will be described through verbal presentation and a sign-up sheet will be passed around for interested participants where they will be asked to provide their name and email address for further communication pertaining to the study in terms of location and scheduled dates. Only interested participants that fill out the sign-up sheet will be contacted regarding participation in the study.

3. EXISTING DATA/SAMPLES:

If the investigator plans to utilize data or samples that are in existence (the investigator will not be recruiting/consenting subjects), describe where the data/samples are housed, how the investigator will gain access to the data/samples, whether the data/samples contain any direct identifiers (e.g., names, address, telephone numbers) or are coded and who will have access to the key to the code (i.e., will the USC investigator have access to key), whether the investigator will sign any data use agreement, and how data will be recorded by USC investigator.

4. CONSENT/ASSENT:

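### The analysis plan lists three F tests without naming the one that decides, lets any of them release within-group t-tests, and leaves baseline hip rotation out as a covariate

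*Protocol*

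**What the plan says.** The Data Analysis paragraph (just before Section E) sets out a sequence. "A one-way ANOVA will be performed first to determine whether the groups are different at baseline, followed by a repeated measure ANOVA", with one within factor and one between-group factor. Of the second model it says "This will reveal the main effects of time, group, and a time by group interaction". The purpose of the F tests is put broadly: "F values will be calculated using SPSS software to assess for any significant differences". The level is fixed once for everything: "Significance will be set at $p < .05$ which establishes a 95% confidence interval". The follow-up rule is "Post-Hoc testing will be conducted if a significant F value is found in order to determine where the differences exist using three Paired t-tests", one per group.

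Section A gives the outcome: "Efficacy will be judged through changes in hip internal rotation range of motion". Section E.1 limits entry: "participants must have less than 30 degrees of hip internal rotation (HIR) in at least one hip". The planned size is 15–20 in each of three groups, 45–60 in all. Baseline rotation appears in the model only as the pre-test level of the time factor; no covariate is named. The text gives no SD, expected gain, pre-post correlation or power.

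**The concern.** The protocol writes its own decision rule, and that rule does not identify a test. Of the three F tests in the repeated-measures ANOVA:

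- **Time by group** compares changes between arms. With one pre-test and one post-test it is the same test as a one-way ANOVA of change scores, is valid at 5%, and matches Section A.
- **Group** averages pre-test and post-test. Because the arms do not differ systematically at pre-test, it sees half the treatment effect.
- **Time** compares no arms. It is significant whenever participants improve on average.

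Any of the three meets the stated trigger. The tests it releases are within-arm, so they cannot show where arms differ. If all arms improve equally, one arm can reach p < .05 and another miss it by chance, and that pattern is easily misread as one treatment working and the other not.

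Two lesser points follow. Subtracting baseline rotation uses it less efficiently than fitting it as a covariate, and precision is scarce with 15–20 per arm. The baseline ANOVA tests a null hypothesis that random allocation makes true, and nothing in the plan depends on its result.

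**Working it through.** **Inputs from the protocol:** three arms; n = 15 or 20 per arm; level .05; one pre and one post value (inferred from the pre-and-post-test wording); outcome is change in rotation. There is no power figure to reproduce; only 3 × 15 = 45 and 3 × 20 = 60 can be checked, and they agree with Section E.1.

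**Assumptions:** SD s = 5 degrees at both times, correlation ρ from 0.3 to 0.9, one hip per participant, no dropout. Gains are 6/6/3 degrees for power, and equal gains of 0, 3, 4 or 6 for error rates. Simulations used 20,000 trials per setting.

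**1. False positives with no effect in any arm.** Accepting either the group or the interaction F: 1 − 0.95² = 9.75% if independent; simulated 9–10%. Accepting any of the three: 1 − 0.95³ = 14.3%; simulated 13.9–14.5%. A single ANCOVA group F stays at about 5%.

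**2. The time effect as trigger.** With an equal 4-degree gain in all arms, the time F is significant in at least 99% of trials.

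**3. Split paired t-tests with equal gains.** Let p be the power of one arm's paired t-test. The chance that the three tests disagree is 1 − p³ − (1 − p)³. For n = 15, ρ = 0.5 and gain 3, the SD of change is 5√(2 × 0.5) = 5, the noncentrality is (3/5)√15 = 2.32, and p = 0.58. The result is 1 − 0.195 − 0.074 = 73%, or 72% in simulation once a significant F is also required. Percentage of trials with a significant F and a split:

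| Equal gain | n | ρ 0.3 | 0.5 | 0.7 | 0.9 |
|---|---|---|---|---|---|
| 3 degrees | 15 | 73 | 72 | 49 | 1 |
| 3 degrees | 20 | 73 | 61 | 25 | 0 |
| 4 degrees | 15 | 65 | 44 | 11 | 0 |
| 4 degrees | 20 | 45 | 22 | 2 | 0 |
| 6 degrees | 15 | 13 | 3 | 0 | 0 |
| 6 degrees | 20 | 3 | 0 | 0 | 0 |

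**4. Efficiency.** Var(change) = 2(1 − ρ)s² and Var(ANCOVA) = (1 − ρ²)s², so the ratio is (1 + ρ)/2: 0.65, 0.75, 0.85, 0.95 at ρ = 0.3, 0.5, 0.7, 0.9. The reciprocals mean that the change score needs 54%, 33%, 18% and 5% more participants.

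**5. Power.** Gains of 6/6/3 deviate from their mean of 5 by 1, 1 and −2, so S = (1 + 1 + 4)/25 = 0.24. The noncentralities are nS/[2(1 − ρ)] for the interaction, nS/[2(1 + ρ)] for the group effect, and nS/(1 − ρ²) for ANCOVA, the last multiplied by 1 − 1/(N − 3), with N the total sample size, for chance baseline imbalance. At n = 15 and ρ = 0.5:

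- interaction: 3.6/1 = 3.6, power about 36%
- group: 3.6/3 = 1.2, power 14%
- ANCOVA: (3.6/0.75)(1 − 1/42) = 4.69, power 45%

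Simulated power in %, as interaction/ANCOVA/group; the formulas agree within about 1 point:

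| n | ρ 0.3 | 0.5 | 0.7 | 0.8 | 0.9 |
|---|---|---|---|---|---|
| 15 | 27/38/16 | 36/45/14 | 56/62/13 | 74/78/12 | 97/97/13 |
| 20 | 34/49/20 | 47/58/18 | 69/76/16 | 87/90/16 | 99/99/15 |

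**6. Effect of the entry limit.** Suppose unselected rotation is normal with mean 28 and SD 5 (assumed). Cutting at 30 leaves variance 0.46 × 25 = 11.5, SD 3.4. With post = slope × pre + error and error variance (1 − slope²) × 25, the ratio is error variance/[error variance + (1 − slope)² × 11.5]:

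- slope 0.5: 18.75/(18.75 + 2.875) = 0.87
- slope 0.7: 12.75/(12.75 + 1.035) = 0.92
- slope 0.9: 4.75/(4.75 + 0.115) = 0.98

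The ANCOVA gain is then 4, 2 and 0 points at n = 15, and 5, 3 and 0 at n = 20.

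**The case against.** The interaction F is a valid test of the outcome that Section A names, so a repeated-measures ANOVA is a legitimate model, and the choice of covariate is often left to a SAP. The efficiency gain rests on assumed values and shrinks to 0–5 points once the entry limit is modelled. The split rates depend heavily on the assumed gain and almost vanish at 6 degrees. The doubled error rate arises only if someone accepts either the group or the interaction F, which the protocol does not say it will do. Part of the protocol, possibly including the measurement schedule, is not in the copy reviewed.

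Much of this stands as a limit on size. The model choice is a matter of efficiency, not validity, and the gain may be small. With more than one post-test, a time point would have to be fixed or a baseline-adjusted mixed model used. If both hips of a participant are analysed, the figures above do not apply.

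None of it rescues the decision rule. That rule is visible text, not a detail deferred to a SAP: an unspecified significant F releases within-arm tests that are meant to locate differences. Section A points towards the interaction, but the analysis paragraph never says so.

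**Conclusion.** The concern holds. The more serious fault is the undefined deciding test, together with a post-hoc step that cannot compare arms. Read loosely, the plan allows about 9–10% false claims of a treatment difference. With modest equal gains it also often produces a misleading mix of significant and non-significant arms (up to 73% of trials at 3 degrees, close to none at 6 degrees or at ρ = 0.9).

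Omitting baseline as a covariate is secondary. Under equal pre and post SDs and gains of 6/6/3, it costs 9–11 power points at n = 15 and 11–15 at n = 20 for ρ of 0.3–0.5. The cost falls to 6–7 points at ρ = 0.7 and about nothing at 0.9, and is 0–5 points if the entry limit narrows the baseline spread as assumed. SDs, gains and correlations are all assumptions, since the protocol supplies none.

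**What to change.** - Make the primary analysis an ANCOVA of post-test rotation on treatment group with continuous baseline rotation as covariate, and its group F the single test of treatment difference at .05. The group contrasts are identical if change is the response, so the Section A outcome is kept. The severity bands are cuts of the same baseline variable.
- Only after a significant group F, report the three baseline-adjusted between-group differences with 95% confidence intervals. Fisher's LSD is sufficient for three groups: simulated family-wise error was 4.7–5.3% with no effect, and 4.4–5.0% for the one null pair when the third arm differs.
- Remove the within-group paired t-tests as post-hoc tests, or label them descriptive.
- Drop the baseline ANOVA and describe baseline values by arm.
- If the repeated-measures ANOVA is kept, name the time-by-group interaction as the only test of treatment difference and the only trigger for between-group comparisons of change. This settles the decision rule but not the efficiency point.

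The cost is wording. No new data are needed and the procedures are standard in SPSS. ANCOVA uses one error degree of freedom: 41 instead of 42 at 15 per group, 56 instead of 57 at 20.

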Our objectives are to quantify the effects of two different modalities of hip mobilization with movement and dynamic stretching in terms of hip internal rotation increases, and to inform current physical therapy practice by filling gaps in the literature surrounding the therapeutic effects of hip mobilization with movement. This study is intended to better equip physical therapists to select the most appropriate evidence-based interventions, thereby increasing the quality of patient care.

B. BACKGROUND AND SIGNIFICANCE

Briefly sketch the background leading to the present application, critically evaluate existing knowledge, and specifically identify the gaps that the project is intended to fill. If the aims of the study are achieved, state how scientific knowledge or clinical practice will be advanced.

Minimal evidence exists comparing the therapeutic effects of variations of mobilization with movement on the hip, but the evidence that does exist shows promising results, with participants gaining increases in functional range of motion from the interventions. There is a significant amount of research regarding mobilization with movement at joints throughout the body, but little that specifically examines internal rotation at the hip. Studies exist that evaluate and compare physical therapist-directed mobilization with movement and self-administered mobilization with movement, with only a single study comparing these two interventions specifically for hip internal rotation, and none which include a dynamic stretching

University of South Carolina Protocol

control group. Stretching is a commonly used physical therapy intervention for range of motion limitations and provides an appropriate foundation and context with which to compare mobilization with movement interventions.

This study will improve physical therapy practice by addressing the nonexistent literature comparing the effects of physical therapist-administered mobilization with movement, self-administered mobilization with movement, and dynamic stretching. Achieving this study's goals and objectives will provide physical therapists with greater evidence to select the most effective treatment interventions to administer to patients, making physical therapy more conducive to functional range of motion gains for the patient.

C. PRELIMINARY STUDIES

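### The only follow-up named after the ANOVA is a pre/post paired t-test within each arm, so no named test or interval shows which intervention does better

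*Protocol*

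**What the plan says.** The Data Analysis paragraph of the protocol plans a one-way ANOVA at baseline and then a repeated-measures ANOVA with time (pre, post) as the within factor and treatment as the between factor. Of the second model it says: "This will reveal the main effects of time, group, and a time by group interaction". It wants to know "whether there is a significant difference between groups and within the same group from pre and post intervention", so change within arms and difference between arms are both stated interests.

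The paragraph then fixes the follow-up. The trigger is "Post-Hoc testing will be conducted if a significant F value is found", without saying which F. The method and its purpose are "in order to determine where the differences exist using three Paired t-tests, one for each group". No comparison between two arms is named, and no interval for a between-arm difference.

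The aims are comparative. Section A states: "The goal of this study is to compare the efficacy of three clinical interventions". Section B describes the gap to be filled as literature "comparing the effects of physical therapist-administered mobilization with movement, self-administered mobilization with movement, and dynamic stretching" and hopes to help therapists "select the most effective treatment interventions to administer to patients". Section E.6 (Potential Benefits) looks ahead to finding self-mobilization as effective as the therapist-performed technique.

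**The concern.** The purpose given to the follow-up and the tests chosen for it do not match. A paired t-test in one arm compares that arm's post-test with its own pre-test. Three such tests answer three separate questions about change. They leave unanswered the three questions the aims raise: therapist-performed against self-mobilization, and each of these against stretching.

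The trigger widens the gap. The repeated-measures model yields three F values, and a time effect shared equally by all arms is enough to open the step. That is harmless for describing change within arms, but it gives no licence to say where arms differ.

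If the paired results are read as the sentence invites, two errors can follow. Arms with equal gains may get different verdicts by chance, although the interaction F shows nothing. Or arms with unequal gains may all be significant, so that the tests do not separate the weaker one.

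This is not a detail that a protocol would leave to a statistical analysis plan. The protocol itself fixes the number of tests, their unit and their purpose.

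**Working it through.** **Inputs.** From the protocol: three arms of about 15 to 20 (3 × 15 = 45, 3 × 20 = 60, matching the stated total of 45–60); significance at .05; two time points. Assumed: two-sided tests, and gains in units of the SD of change (set to 1), because the protocol gives no effect size or SD. There is no stated power figure to reproduce. Paired results below are for 15 / 20 per arm.

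**Formulas.** With two time points, the time-by-group F equals the F of a one-way ANOVA on change (post minus pre). With SD of change 1 in every arm:
- interaction F = n × variance of the three mean gains, on 2 and 3(n−1) df;
- time F = 3n × (overall mean gain)², on 1 and 3(n−1) df;
- paired t = gain × √n, on n−1 df;
- 95% CI half-width of a between-arm contrast = t(.975, 3(n−1)) × √(2/n) = 0.737 / 0.633.

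**Example (a): n = 15, observed gains 2, 2, 1.** The variance of the means is 1/3, so the interaction F(2,42) = 15/3 = 5.00, p = .011. The smallest paired t is 1 × √15 = 3.87, p = .0017, so all three paired tests are significant. The contrast between a better arm and the weaker arm is 1.00 (95% CI 0.26 to 1.74), p = .009. Only the contrast separates them.

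**Example (b): n = 15, observed gains 0.60, 0.60, 0.45.** Time F(1,42) = 45 × 0.55² = 13.6, p = .0006, so the follow-up opens. Paired p = .036, .036 and .103: two arms pass and one fails. Interaction F = 15 × 0.0075 = 0.11, p = .89. The contrast is 0.15 (−0.59 to 0.89), p = .68. The verdicts split although nothing separates the arms.

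**Equal true gains, simulated** (40,000 runs, pre/post correlation 0.6). Chance that the follow-up opens, the paired verdicts split and the interaction F is non-significant:

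| Gain in every arm (SD) | n = 15 | n = 20 |
|---|---|---|
| 0.3 | 34% | 44% |
| 0.5 | 67% | 68% |
| 0.65 | 63% | 46% |
| 0.8 | 40% | 18% |
| 1.0 | 12% | 2% |
| 1.5 | 0% | 0% |

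Closed-form check at 0.5: the power of one paired test is p = 0.438 / 0.565, and the chance of a split is 1 − p³ − (1−p)³ = 0.74 at both sizes. Requiring in addition an open step and a null interaction brings this down to the simulated 67% / 68%.

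**Unequal true gains, simulated, given a significant interaction F** (significant in 78–79% / 90% of runs). The paired pattern counts as right if the two better arms are significant and the weaker is not. The contrast pattern counts as right if both true differences are significant and the equal pair is not.

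| True gains (SD) | Paired pattern right | Contrast pattern right |
|---|---|---|
| 2, 2, 1 | 6% / 1% | 78% / 85% |
| 1.5, 1.5, 0.5 | 66% / 48% | 78% / 85% |
| 1.25, 1.25, 0.25 | 92% / 87% | 78% / 85% |
| 1, 1, 0 | 89% / 95% | 78% / 85% |

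The gap between arms is 1 SD in every row, so the contrasts perform alike throughout. The paired tests track how far the weakest arm lies from zero change, not the gap between arms.

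**Error rate of the remedy** (100,000 runs). Testing pairwise contrasts at .05 only after a significant interaction F gives a familywise error of 5.0% / 5.0% when all arms are equal. When one arm differs by 0.5, 1 or 3 SD, a false claim on the equal pair occurs in 3.9% / 4.1%, 5.0% / 5.0% and 5.0% / 5.0%. Without the gate, unadjusted contrasts give 12.1% at both sizes when all arms are equal.

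**The case against.** The plan does contain a valid between-arm test. An analyst who reports a non-significant interaction F would report no difference in change, so the split verdicts mislead only someone who overrides that F. The protocol never says it will rank arms by their paired p-values. The score for the paired tests embodies that unstated rule: in the first three unequal-gain scenarios the weaker arm truly improves, so a correct rejection counts as wrong. Nor is the weaker arm invisible, since arm means can be subtracted; in these scenarios, given a significant interaction, it has the lowest observed mean gain in more than 99.8% of runs. Per-arm tests of time are also an ordinary way to describe an interaction, and within-arm change is a stated interest. Finally, other multiplicity methods would serve as well as the one proposed.

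Most of this stands as a limit on size. The percentages describe what happens if the paired tests are used to locate differences between arms, and no point in the assumed range is favoured by the protocol. The paired tests are legitimate for change within arms. But the core remains: the named follow-up attaches no test or interval to any difference between two arms, and ordering the observed means does not supply one. The choice of gate is one valid option among several; what is needed is that some between-arm contrast be named and tied to the interaction.

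**Conclusion.** The concern holds. The overall time-by-group test is sound, but the follow-up cannot do the job the protocol gives it, and its trigger is not restricted to the F that compares change between arms. This conclusion rests on the wording alone and needs no assumed effect size.

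The practical harm does depend on assumptions: on the gains, and on the paired results being read as evidence about differences between arms. It is large for moderate equal gains and for unequal gains where every arm clearly improves. It is small or absent when equal gains are large, or when the weakest arm changes little. The point should be fixed before the data are analysed; it does not undermine the design.

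**What to change.** Replace the last sentence of the Data Analysis paragraph with wording such as:

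> The between-arm question is tested by the time-by-group F at .05. If, and only if, that F is significant, the three pairwise between-arm differences in change in hip internal rotation are tested at .05 using the pooled error term. The three differences are reported with 95% CIs whatever the F result; these CIs are not adjusted for multiplicity and are not used to claim significance. Within-arm paired t-tests describe change in each arm only and are not used to compare arms.

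In SPSS this is a one-way ANOVA of change with LSD post-hoc output. An ANCOVA of post-test on baseline could replace that F throughout, provided one route is named in advance.

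The cost is a change of wording and slightly more output; no new data are needed. The intervals will be wide at this sample size: by the normal approximation, the difference detectable with 80% power in an unadjusted contrast is (1.96 + 0.84) × √(2/n), about 1.02 SD at 15 per arm and 0.89 SD at 20. A non-significant contrast would therefore not show that self-mobilization is as effective as the therapist-performed technique; that claim would need a margin stated in advance.

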All participants will have to sign an informed consent form in order to participate in the study which outlines the expected timeline of the study, the requirements of participation, and the option to opt out of the study at any time if someone chooses to do so. The informed consent form has been uploaded onto the eIRB at this time for review.

5. POTENTIAL RISKS:

There are minimal risks that can occur during the study as we are only performing a mobilization with movement at the hip joint using external measures such as a Mulligan mobilization belt. The only side effects that can occur from performing the technique is increased range of motion at the hip or possible discomfort from increased range of motion at the hip. If any participants experiences any pain or discomfort during the interventions provided, the technique will be stopped and will be re-assessed before continuing with that specific participant to limit any source of discomfort.

6. POTENTIAL BENEFITS:

The potential benefits for participants is increased range of motion at the hip, specifically for hip internal rotation. The benefit to others includes the potential that clinicians may be able to assign a self-mobilization with movement for patients at home if it proves to be just as effective as the therapist-performed-mobilization with movement. This would allow clinicians to focus on other interventions while patients are in the clinic and hopefully have better long-term outcomes.

University of South Carolina Protocol

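### E.6 looks ahead to finding self-mobilization as effective as therapist mobilization, but the analysis described tests only for difference and could not support that finding

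*Protocol*

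**What the plan says.** Section A of the protocol states a comparative goal: "The goal of this study is to compare the efficacy of three clinical interventions intended to treat hip dysfunctions such as hip osteoarthritis". It contains no equivalence or non-inferiority hypothesis.

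Section E.6 (Potential Benefits) adds a specific hope: "The benefit to others includes the potential that clinicians may be able to assign a self-mobilization with movement for patients at home", on the condition "if it proves to be just as effective as the therapist-performed-mobilization with movement".

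The Data Analysis paragraph sets the error level: "Significance will be set at $p < .05$ which establishes a 95% confidence interval". After a baseline one-way ANOVA comes a repeated measures ANOVA with a within-subject and a between-group factor: "This will reveal the main effects of time, group, and a time by group interaction". The purpose of the test is stated plainly: "F values will be calculated using SPSS software to assess for any significant differences". If an F is significant, post-hoc testing consists of three paired t-tests, one in each arm.

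On size, the protocol proposes roughly 15 to 20 people per arm, and E.1 (Target Population) says: "Anticipated sample size is between 45-60 participants".

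**The concern.** To show that one treatment is as effective as another, the data must rule out a disadvantage large enough to matter. That needs an estimate of the difference between the two arms, its confidence interval, and a criterion to hold the interval against. The analysis described supplies none of these for self versus therapist mobilization. It asks whether some difference exists among three arms or over time, and then whether each arm changed from its own baseline.

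A small trial can fail to find a difference because the arms are alike or because it is imprecise, and the described output cannot tell these apart. The question in E.6 is a practical one, whether home self-treatment could stand in for therapist time. An unsupported answer could travel further than the data allow.

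**Working it through.** **Step 1. The protocol's own figure.** 3 × 15 = 45 and 3 × 20 = 60, which agrees with the total in E.1. The text available gives no SD, effect size, power or margin, so this total cannot be traced to a power calculation.

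**Step 2. Which described output could answer E.6?**

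| Output | What it addresses | Does it support equal effectiveness? |
|---|---|---|
| Time effect | Average change over all arms | No, it does not compare arms |
| Group effect | Arm means averaged over both time points | No, it is a difference test across three arms |
| Time-by-group effect | Whether change differs somewhere among three arms | No. Non-significance does not bound the self-versus-therapist gap, and significance may come from stretching |
| Paired t-test in each arm | Change from that arm's own baseline | No. Two arms can both improve by very different amounts |

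No row estimates self minus therapist.

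**Step 3. Precision of the missing contrast.** Assumptions: SD of the pre-to-post change 5 to 8 degrees, n = 15 or 20 per arm, error variance pooled over three arms (df = 3(n − 1) = 42 or 57), two-sided 5%, no dropout, no multiplicity adjustment.

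Half-width = t(0.975, df) × SD × √(2/n).

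- n = 15: 2.018 × 0.3651 = 0.737 SD
- n = 20: 2.002 × 0.3162 = 0.633 SD

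P(non-significant) comes from the noncentral t with noncentrality δ / (SD × √(2/n)), where δ is the true deficit of self-mobilization. For example, at SD 8 and n = 15 the noncentrality for δ = 5 is 5 / 2.921 = 1.71.

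| SD (degrees) | Half-width, n = 15 / 20 | Non-significant, δ = 3, n = 15 / 20 | Non-significant, δ = 5, n = 15 / 20 |
|---|---|---|---|
| 5 | 3.7 / 3.2 | 64% / 54% | 24% / 13% |
| 6 | 4.4 / 3.8 | 73% / 66% | 39% / 26% |
| 8 | 5.9 / 5.1 | 83% / 79% | 61% / 51% |

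The deficits of 3 and 5 degrees are illustrative values, not proposed margins.

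**Step 4. The omnibus F that the protocol does plan.** With two time points, the time-by-group F equals a one-way ANOVA on change scores, with noncentrality λ = n × Σ(mean − grand mean)² / SD². Take SD 8 and a 5-degree deficit of self against therapist.

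- Stretching midway between them: Σ = 12.5, λ = 2.93 (n = 15) or 3.91 (n = 20). F is non-significant in 71% or 61% of trials.
- Stretching a further 5 degrees worse than self: Σ = 50, λ = 11.72 or 15.62. F is non-significant in 15% or 6%.

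The same self-versus-therapist gap gives very different F results depending on the third arm, so F is no guide to that gap.

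**Step 5. A hypothetical result at SD 8, n = 15.** Suppose the therapist arm gains 10 degrees and the self arm 5. The within-arm SE is 8/√15 = 2.07, so the paired t values are 4.84 and 2.42. Both exceed t(0.975, 14) = 2.145, so both arms improve significantly. The direct contrast is 5 / 2.921 = 1.71, below 2.018, so it is non-significant. Its interval for self minus therapist is −5 ± 5.9, or −10.9 to 0.9 degrees. Both tempting signs of equality appear while one arm gains twice as much as the other.

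**The case against.** The strongest reply is that E.6 is a benefit statement in the human-subjects section. It is conditional, and the aims speak only of comparing efficacy and quantifying effects, for which a difference test is reasonable. This stands. A reader might infer that the protocol plans to recommend home self-mobilization, but the text says only that clinicians may be able to assign it if a condition is met.

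A reader might also infer that a non-significant result will be read as equality. No sentence says so. What can be said is that the analysis described offers no valid route to the E.6 conclusion.

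Nor does the plan necessarily stop when the arms look alike. Post-hoc testing follows a significant F without saying which of the three effects is meant, so a time effect alone could trigger the paired t-tests. That does not help E.6, because those tests are within-group.

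The figures in Step 3 concern a pairwise contrast that the protocol does not plan, under assumed SDs. They illustrate imprecision and are not operating characteristics of the stated procedure. At SD 5 a 5-degree deficit would be detected in 76% to 87% of trials, so the picture is not uniformly bleak.

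It is tempting to use the roughly 5-degree severity bands as a margin. They classify baseline limitation and say nothing about what loss of benefit is acceptable.

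Finally, margins and contrasts are often left to a statistical analysis plan, one may exist here, and part of the protocol was not available. The point therefore does not rest on absence alone. The protocol itself states the hoped-for conclusion and itself fixes the test, the error level and the post-hoc procedure, and these do not fit together.

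**Conclusion.** The concern holds as a mismatch between two stated parts of the protocol. E.6 anticipates a conclusion of equal effectiveness. Data Analysis describes only difference tests and within-arm tests, and neither a non-significant F nor improvement in both arms would establish that conclusion. This part needs no numerical assumption.

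The size is illustrative. At 15 to 20 per arm and an assumed SD of change of 5 to 8 degrees, the self-minus-therapist interval would extend about 3.2 to 5.9 degrees either side of the estimate. A true 5-degree deficit would go undetected by a direct contrast in about 13% to 61% of trials. A different SD would move these figures. The point is worth correcting before data collection because the remedy is cheap.

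**What to change.** In Data Analysis, add that the self-minus-therapist difference in change in hip internal rotation will be reported with its 95% CI whatever the F result, and that a non-significant difference will not be interpreted as equal effectiveness.

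Then do one of the following:

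- Before data collection, fix a clinically justified margin and conclude equal effectiveness only if the CI excludes a disadvantage larger than that margin. The value and its justification are for the investigators, and the severity bands are not a basis for it.
- Reword the condition in E.6 to: *if the confidence interval rules out a clinically important disadvantage*.

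The cost is a few sentences and one interval from data already being collected, with no extra participants. The downside is that the trial may be unable to make the claim. By the normal approximation, with truly equal arms and a one-sided 2.5% level, the smallest margin giving 80% power is (1.96 + 0.84) × √(2/n) SD. That is 1.02 SD at n = 15 and 0.89 SD at n = 20, or from 0.89 × 5 ≈ 4.4 degrees to 1.02 × 8 ≈ 8.2 degrees over the assumed SDs. It is better to know this beforehand.
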